## DOCUMENT CHANGE HISTORY

Version	Originator	Description of Change(s)	Date
1.0	[REDACTED]	Original Protocol	20-Aug-2020

## 1 Introduction

---

CooperVision is evaluating the clinical performance of Orion (riofilcon A with DAB) Test lens compared to Gemini (██████) Control lens when worn on a daily wear, daily disposable modality in a randomized, bilateral crossover dispensing study.

## 2 Study Objective

---

This is a feasibility study to evaluate the clinical performance of a new silicone hydrogel formulation lens (Orion) in comparison with Gemini A ██████ over a period of two weeks of wear.

The primary variables of interest are:

- Vision

The secondary variables of interest are:

- Comfort/comfort preference
- Surface wettability performance
- Lens fit
- Lens handling
- Anterior ocular health

### 2.1 Study Hypothesis

---

The primary hypothesis is that there will be no difference in vision performance between the Orion Test lens and the Gemini Control lens.

The secondary hypothesis is that there will be no difference in performance between the Orion Test lens and the Gemini Control lens for any of the secondary variables.

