### 7.3.2 Visit 1b: Dispensing Visit (Pair 1)

*Dispensing visit may occur on same day as Visit 1a. If Visit 1b is conducted on a different day to Visit 1a, slit lamp biomicroscopy should be conducted again to confirm eligibility.*

- HVID (mm) and palpebral aperture size (mm) measurements using slit lamp oculars.
- The first study pair of contact lenses will be selected by the investigator according to the randomization table [REDACTED] insertion by the subjects. Subjects will be dispensed the lens power nearest to their refractive error requirement.
- Lenses should be allowed to settle for 10 minutes.
- An initial fit assessment will be made to ensure lens fit is acceptable (Y/N). The subject should be discontinued and exited if the lens fit is found unacceptable and the primary reason for poor fit recorded on the CRF and video footage of the fit collected.
- Monocular spherical over-refraction (SOR) will be conducted to determine if a different lens power is required.
- Monocular and binocular **HIHC** and **HILC** distance logMAR visual acuities will be recorded (SOR will be used if the subject is wearing monovision).
- Final lenses will be inserted and allowed to settle for a further 10 minutes, if applicable.

- [REDACTED]

- [REDACTED]
- [REDACTED]
- [REDACTED]
- [REDACTED]
- [REDACTED]
- [REDACTED]
- [REDACTED]
- [REDACTED]
- [REDACTED]

- Lens surface will then be assessed and graded after settling per guidelines detailed in the CVI grading scales ( [REDACTED] )
  - [REDACTED]
  - Wettability (0-4 scale)
  - [REDACTED]
  - [REDACTED]
- Lens fit will then be assessed and graded according to the guidelines detailed in CVI Grading scales ( [REDACTED] ).
  - Lens centration (0.1mm steps)
  - [REDACTED]
  - Post-blink movement (0.1mm steps)
  - Mobility rating (0.50 steps)
  - Overall lens movement (-2 to +2 scale)
  - Overall lens fit acceptance and investigator reason, if unacceptable (0.25 steps). Video will be recorded in the event of poor fit. Video will be recorded in the event of poor fit.
- The subject will be instructed to wear the study lenses for a minimum of 8 hours per day / 6 days per week.
- The subject will be dispensed adequate lenses (including spares) to last them until the next study visit.
- The subject will be discharged and scheduled to return for Visit 2 within the required study visit window.

### 7.3.3 Visit 2: Two-Week Follow-up Pair 1 (-1/+4 days) & Dispensing Pair 2

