*Subjects will be asked to wear lenses for **at least 3 hours** prior to the visit appointment.*

- Subjective responses will be collected per the Final Questionnaire [REDACTED] including:
  - Overall satisfaction (7-point Likert scale)
  - Comfort satisfaction & comfort rating (7-point Likert & 100-point scales)
  - [REDACTED]
  - [REDACTED]
  - [REDACTED]
  - [REDACTED]
  - [REDACTED]
  - [REDACTED]
  - [REDACTED]

- [REDACTED]
  - Lens handling (7-point Likert & 100-point scales)
  - [REDACTED]
  - [REDACTED]
  - Lens holding/handling (5-point Likert scales)
  - Vision (7-point Likert & 100-point scales)
- The following information will be collected from the subject by the investigator:
    - Wear time at visit (hours).
    - Average time of insertion and removal during previous week, i.e. average time (hours).
    - Maximum wear time during previous week (hours).
    - Average time of day lenses become uncomfortable, if at all, i.e. average comfortable wear time (hours).
    - Use and frequency of comfort / re-wetting drops during past week (if any).
  - Monocular and binocular **HIHC** and **HILC** distance logMAR visual acuities will be recorded (a spherical over-refraction will be performed for the distance eye and recorded first if the subject is wearing monovision).
  - Lens surface will then be assessed and graded per guidelines detailed in the CVI grading scales [REDACTED]
    - [REDACTED]
    - Wettability (0-4 scale)
    - [REDACTED]
    - [REDACTED]
  - Lens fit will then be assessed and graded according to the guidelines detailed in CVI Grading scales [REDACTED]
    - Lens centration (0.1mm steps)
    - [REDACTED]
    - Post-blink movement (0.1mm steps)
    - Mobility rating (0.50 steps)
    - Overall lens movement (-2 to +2 scale)
    - Overall lens fit acceptance and investigator reason, if unacceptable (0.25 steps). Video will be recorded in the event of poor fit.
  - The lenses will be removed and stored in either an unbuffered or phosphate buffered (not borate) saline for return to the Sponsor.

- Slit lamp biomicroscopy will be assessed according to the CVI approved study biomicroscopy CRF [REDACTED]

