### Dispensing Visit (Pair 2)

- The subject will undergo a saline washout.
- The second study pair of contact lenses will be selected by the investigator according to the randomization table [REDACTED] for insertion by the subjects. Subjects will be dispensed the lens power nearest to their refractive error requirement.
- Lenses should be allowed to settle for 10 minutes.
- An initial fit assessment will be made to ensure lens fit is acceptable (Y/N). The subject should be discontinued and exited if the lens fit is found unacceptable and the primary reason for poor fit recorded on the CRF and video footage of the fit collected.
- Monocular spherical over-refraction (SOR) will be conducted to determine if a different lens power is required.
- Monocular and binocular **HIHC** and **HILC** distance logMAR visual acuities will be recorded (SOR will be used if the subject is wearing monovision).
- Final lenses will be inserted and allowed to settle for a further 10 minutes, if applicable.
- Subjective responses will be collected per the Post-Settling Questionnaire [REDACTED], including:
  - [REDACTED]
  - [REDACTED]
  - [REDACTED]
  - [REDACTED]
  - [REDACTED]
  - [REDACTED]
  - [REDACTED]
  - [REDACTED]
  - Lens movement/awareness (5-point Likert scales)
  - Vision (7-point Likert & 100-point scales)
- Lens surface will then be assessed and graded after settling per guidelines detailed in the CVI grading scales [REDACTED]
  - [REDACTED]
  - Wettability (0-4 scale)
  - [REDACTED]
  - [REDACTED]

- Lens fit will then be assessed and graded according to the guidelines detailed in CVI Grading scales ( [REDACTED] ).
  - Lens centration (0.1mm steps)
  - [REDACTED]
  - Post-blink movement (0.1mm steps)
  - Mobility rating (0.50 steps)
  - Overall lens movement (-2 to +2 scale)
  - Overall lens fit acceptance and investigator reason, if unacceptable (0.25 steps).  
Video will be recorded in the event of poor fit.
- The subject will be instructed to wear the study lenses for a minimum of 8 hours per day / 6 days per week.
- The subject will be dispensed adequate lenses (including spares) to last them until the next study visit.
- The subject will be discharged and scheduled to return for Visit 3 within the required study visit window.

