  - Exit HIHC monocular distance logMAR visual acuities will be recorded with baseline spherocylindrical refraction in place (OD/OS).
  - The subject will be discharged and will sign the exit statement.

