### 10.1 Sample size

---

Based on historical data, a sample size of 14 completing subjects is sufficient to detect a non-inferiority margin of 0.1 logMAR for the primary variable, visual acuity, assuming  $\alpha=0.05$  and a power of 80% (Table 3).

Table 3: Primary variable (acuity) sample size calculation

Non-inferiority margin for logMAR visual acuity	Mean individual standard deviation	Sample size, Power 80% ( $p = 0.05$ )
-0.1	0.07	14

Based on historical data, a sample size of 53 completing subjects is sufficient to detect a non-inferiority margin of -0.75 for the secondary variable, comfort, assuming  $\alpha=0.05$  and a power of 80% (Table 4).

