## 10.2 Statistical analysis

---

Summary statistics will be produced (e.g. mean, standard deviation). Paired t-test will be used to compare slit lamp biomicroscopy, lens fit and subjective scores between study lens types. Repeated Measures Analysis of Variance (ANOVA) or paired analysis will be used to compare the variables between study visits. The critical alpha level for statistical significance will be set at  $p \leq 0.05$ , with adjustment for multiple comparisons.

All participants who were evaluated will be used in the analysis. In the event of missing data, individual data points will be excluded in the analysis and not extrapolated from the collected data.

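### The 0.1 logMAR margin is set for a single acuity variable, but each lens has six two-week acuity readings (and six more at dispensing) and nothing says which must meet it

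*Combined protocol and SAP*

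**What the plan says.** - Section 2 gives the primary variable as vision, in one word. Section 2.1 states the primary hypothesis as "there will be no difference in vision performance between the Orion Test lens and the Gemini Control lens", with no margin.
- Section 10.1 narrows this to acuity and sizes the study against "a non-inferiority margin of 0.1 logMAR for the primary variable, visual acuity". Table 3 gives one margin, one SD (0.07) and one sample size (14).
- Sections 7.3.2 to 7.3.4 collect acuity as a set. At dispensing of Pair 1, "Monocular and binocular HIHC and HILC distance logMAR visual acuities will be recorded", and the same set is taken at the Pair 1 follow-up, at dispensing of Pair 2 and at the Pair 2 follow-up. The exit acuity item in section 7.3.4 shows that monocular means each eye separately.
- Vision is also rated by the subject on 7-point and 100-point scales.
- Section 10.2 assigns the between-lens paired t-test to slit lamp findings, lens fit and subjective scores. Acuity is not on that list. A repeated-measures or paired analysis covers unnamed variables between visits. Significance is set at 0.05 "with adjustment for multiple comparisons", with no method and no family of tests.

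None of these statements is redacted on this point.

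**The concern.** A margin becomes a success criterion only when the plan says which estimate is compared with it. Here one margin faces several acuity estimates, and the plan gives no rule: not a single named reading, not all of them, not any of them. Two analysts following the plan could reach opposite primary conclusions from the same data, for example if the Test lens matched the Control on high contrast and fell short on low contrast.

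Section 10.2 does not close the gap. Its tests look for differences, while the claim of interest is that the lenses match; section 3.1 gives matching the Control's performance as the aim. Failing to find a difference, at a stricter alpha or any other, does not establish a match within 0.1 logMAR. Adding a margin test would not settle the matter alone, because the result would still depend on the reading selected.

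**Working it through.** **1. The plan's own figure.** Table 3: margin 0.1, SD 0.07, alpha 0.05, power 80%. The two-group formula at one-sided 0.05 gives n per group = 2 × (1.645 + 0.842)² × 0.07² / 0.1² = 2 × 6.18 × 0.49 = 6.06, rounded up to 7, so 14 in total. The stated 14 is reproduced, but as a two-group total. Paired non-inferiority calculations for the crossover, at 80% power and one-sided 0.05, give 5 (SD of the difference 0.07) or 8 (SD 0.07 × √2). The calculation covers one acuity variable.

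**2. Number of readings per lens.** 3 (right, left, binocular) × 2 (HIHC, HILC) = 6 at two weeks. With dispensing, 6 × 2 = 12.

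**3. Assumptions.** Completers: 60 (section 7.1). Table 3 does not say whether 0.07 is the SD of a single reading or of the paired difference; I take 0.07 × √2 = 0.099 for the difference. Section 10.1 gives no sidedness; I use one-sided 0.05. The documents give no correlation between readings; I use 0.3 to 0.9, equal for all pairs.

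**4. One reading.** A reading passes if mean + t × SD/√n < 0.1. With t(59) = 1.671 and SE = 0.099/√60 = 0.0128, the half-width is 0.021, so the observed mean must be below about 0.079. As a hypothetical case, suppose the Test lens is truly 0.02 worse on HIHC and 0.12 worse on HILC. HIHC then passes in over 99.9% of trials and HILC in about 0.1%, so the chart chosen decides the conclusion.

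**5. Any one of six may carry the claim, true deficit 0.1 on all.** If the readings were independent, the chance of at least one false pass would be 1 − 0.95⁶ = 26%. By simulation with correlated readings:

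| Rule | Correlation 0.9 | Correlation 0.3 |
|---|---|---|
| Any of 6, unadjusted | 10% | 22% |
| Any of 6, Bonferroni | 2% | about 4.5% |

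**6. All six must pass, n=60, one-sided 0.05, same true deficit on every reading.** HIHC difference SD is 0.099 throughout. The documents give no separate SD for HILC, so it is varied. Ranges are over correlations 0.3 to 0.9.

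| HILC difference SD | True deficit 0 | 0.02 | 0.04 |
|---|---|---|---|
| 0.099 | about 100% | about 100% | about 99% or more |
| 0.15 | 99.8% or more | 98–99% | 79–88% |
| 0.20 | 93–98% | 81–88% | 47–65% |

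Hand check of the first row at 0.04: (0.079 − 0.04)/0.0128 is about 3.0, so each reading fails in roughly 0.14% of trials. Six readings together fail in at most 6 × 0.14% = 0.8%.

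**The case against.** **Feasibility study.** Section 2 describes it so, and that lowers the stakes. Section 10.1 nonetheless sets a margin, alpha and power for a primary variable, so a success rule is needed.

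**Twelve readings overstates the choice.** This stands in part. Section 2 frames the comparison over two weeks of wear. In sections 7.3.2 and 7.3.3, dispensing acuity is listed after the over-refraction that checks lens power and before the final lenses go in, so it looks like a fitting check. Six is the natural count, but no text says so, and six still need a rule.

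**Error inflation.** A reader might infer that the false non-inferiority rate is well above 5% under the plan. The documents do not support that: section 10.2 does call for an adjustment, and Bonferroni would control the rate. What remains is that neither method nor family is stated, so control is possible but not assured.

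**Direction of the adjustment.** A reader might also infer that the multiplicity adjustment makes the hypothesised result easier to reach. With a difference test it would: at n=60 and SD 0.099, Bonferroni over 12 readings lowers detection of a true 0.04 deficit from 87% to 56%. But section 10.2 does not assign acuity to its between-lens difference tests, and section 10.1 frames acuity as non-inferiority, where adjusted limits make success harder. A 0.04 deficit also lies inside the plan's own margin, and a 0.1 deficit would still be detected almost always. The inference holds only because no margin test is described.

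**Margin for low contrast.** Section 10.1 ties neither the margin nor the SD to HILC. This stands, and is a reason to offer a single named reading as an alternative.

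**Conclusion.** The gap is real and should be corrected. The primary acuity reading and the rule for meeting the 0.1 logMAR margin are undefined, across six two-week readings and six dispensing readings per lens. The analysis in section 10.2 supplies no test that could support a claim of matching.

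The size depends on how the gap is filled. If any one of six readings sufficed without adjustment, false non-inferiority would be about 10–22%; with Bonferroni, about 2–4.5%. Both rest on the assumed SD of 0.099, 60 completers, one-sided 0.05 and correlations of 0.9 to 0.3. The main harm is that the endpoint can be chosen after the data are seen. With about 60 completers, a margin-sized loss on a reading that is actually tested would not be missed.

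**What to change.** Before unmasking, state in sections 2.1 and 10.2 that the primary variable is logMAR acuity at the two-week visits. Non-inferiority is concluded only if the upper confidence limit for Test minus Control is below 0.1 logMAR, at a stated one-sided level. Choose one of two rules:

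- **All six** two-week readings (HIHC and HILC, each right, left and binocular) must pass. No alpha adjustment is needed, because every reading has to succeed.
- **One reading** named in advance must pass, with the other five secondary.

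Under either rule, make dispensing-day acuity and the subjective vision ratings secondary.

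The change takes a few sentences and no extra subjects or data. The all-six rule is stricter. At n=60 it costs little if every difference SD is near 0.099, but if low-contrast differences have SD 0.15, power falls to 79–88% at a true deficit of 0.04, and it is lower still at SD 0.20. A one-sided level of 0.025 would lower these further. If the sponsor's historical data show low contrast to be that variable, a single named reading keeps more power, at the price of a narrower claim.

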## 3 Study Design

---

This will be a double-masked, randomized, bilateral, two-week crossover, dispensing study, comparing the Orion Test lens against Gemini Control lens, such that each daily replacement lens type will be worn on a daily wear, single use basis for two weeks each. Each subject will be randomized to wear either the Test lenses or the Control lenses potentially as an unmatched pair (with regards to power), according to a predetermined randomization schedule. All lenses will be

replaced daily. Electronic (e.g. email or SMS text survey link) comfort questionnaires will be administered during the course of the study.

It is anticipated that this study will involve up to 4 scheduled visits:

- Visit 1a: Enrollment / Screening / Baseline Visit (Day 0)
- Visit 1b: Dispensing of Pair 1 (Day 0)
- Visit 2: Two-week follow-up of Pair 1 (-1/+4 days) and Dispensing of Pair 2
- Visit 3: Two-week follow-up of Pair 2 (-1/+4 days) and Exit

### **3.1 Study Design & Comparator Justification**

---

The study design was chosen since the influence of confounding covariates is reduced in crossover designs, as each subject acts as his or her own control. Crossover study designs are also statistically more efficient.

The choice of comparator was made since the aim of the project is to match the clinical performance of the Gemini (Acquiane) lens, which is CE-marked / already approved in Europe.

## **4 Ethics Review / Statement of Compliance**

---

### **4.1 Relevant Standards / Guidelines**

---

This protocol has been developed in accordance with 21 CFR Part 812: Investigational Device Exemptions and with the ethical principles of:

- ISO 14155 Clinical Investigation of Medical Devices for Human Subjects
- Declaration of Helsinki

### **4.2 Institutional Review Board**

---

This study will be conducted in accordance with Institutional Review Board regulations (U.S. 21CFR Part 56.103) or applicable IEC regulations. Copies of all IRB/IEC correspondence with the investigator/sponsor will be kept on file.

The conduct of this study will be approved by Sterling Institutional Review Board. Approval will be received prior to undertaking the study. Any additional requirements imposed by the Ethics Committee/IRB or separate regulatory authority will be followed.

### **4.3 Informed Consent**

---

Informed consent shall be obtained in writing from the subject and the process shall be documented before any procedure specific to the clinical investigation is carried out.

## **5 Clinical Trial Registration**

---

This Study will be registered with ClinicalTrials.gov in accordance with Section 801 of the Food and Drug Administration Act (FDAA) which mandates the registration of certain clinical trials of drugs and medical devices.

## **6 Potential Risks and Benefits to Human Subjects**

---

There might not be direct benefits to the subjects in this study. However, participation in a study may contribute to scientific research information that may be used in the development of new contact lens products. In addition, subjects will receive an examination of the front part of their eyes and may have the opportunity to try a different type of soft contact lenses and/or different lens care products at no cost to them.

This study is considered to be a non-significant risk study based on United State Food and Drug administration (FDA) and International Standards Organization (ISO) guidelines due to the daily wear nature of the study. The risks to the subjects are also reduced based on the results of biocompatibility testing.

Complications that may occur during the wearing of contact lenses include discomfort, dryness, aching or itching eyes, excessive tearing, discharge, hyperemia and variable or blurred vision. More serious risks may include photophobia, iritis, corneal edema or eye infection. Although contact lens-related infections are very infrequent, the possibility does exist. The incidence of infection due to day-wear soft lenses is 0.035%. Almost always an infection will occur only in one eye. This risk is assumed by 35-million Americans who currently wear contact lenses.

Routine clinical procedures including auto-refraction, auto-keratometry, visual acuity, anterior ocular health assessment, and contact lens fitting will be used. In addition, high magnification imaging of the lens fit may be made using 35 mm or digital cameras, in vivo confocal microscopy, and/or specular microscopy.

## 7 Materials and Methods

---

### 7.1 Participants

---

Up to 70 subjects will be enrolled and dispensed in order for approximately 60 subjects to complete the study. Each subject will be given a unique ID number. ID numbers will not be reused in event of screen failure or discontinuation. Additionally, all subjects must meet the study inclusion and exclusion criteria listed below.

#### Inclusion criteria

A person is eligible for inclusion in the study if he/she:

- Is at least 18 years of age and has full legal capacity to volunteer.
- Is no greater than 55 years of age.
- Has read and understood the information consent letter.
- Is willing and able to follow instructions and maintain the appointment schedule.
- Is an adapted soft contact lens wearer having worn lenses for a minimum of 4 weeks prior to the study.
- Has spectacle cylinder  $\leq 1.00D$  in both eyes.
- Has spherical contact lens power requirement between  $-1.00D$  and  $-6.00D$  in both eyes.
- Has manifest refraction visual acuities (VA) equal to or better than logMAR equivalent of 20/20 in each eye.
- Wears CLs in both eyes (monovision acceptable, but not monofit)
- Has clear corneas and no active ocular disease.
- Has not worn lenses for at least 12 hours before the examination.
- Is willing to wear the study contact lenses for a minimum 8 hours per day/6 days per week

